#### Data protection

The Data Protection Directive is the cornerstone of EU personal data protection. However, in January 2012 the European Commission proposed a comprehensive reform of the data protection rules, to update and modernise the principles enshrined in the 1995 Data Protection Directive to guarantee privacy rights in the future. Central to these proposals is a new regulation (EU General Data Protection Regulation (GDPR) 2018), specifically Articles 12 (1), 13 (1) and 89 (1), which to set out a general EU framework for data protection and which includes special rules on the collection and use of personal data for medical research and public health purposes. Emerging legislation will be monitored to ensure the long-term and on-going legitimacy of COMBACTE-CDI approaches to data privacy.

The following general principles will apply to all research conducted in COMBACTE-CDI.

Data handling will comply with current national and EU legislation, including:

- Personally Identifiable Information (PII) is adequately protected;
- Anonymisation/de-identification is conducted appropriately;
- Ethical review is completed as required.

Each COMBACTE-CDI member will be responsible for the confidentiality and security of personal identifiable information and for complying with their own SOPs and any shared COMBACTE-CDI SOPs.

In general terms, appropriate data protection principles will be observed, including:

- Data are fairly and lawfully processed;
- The amount of data collected is relevant and not excessive;
- All reasonable efforts are taken to ensure data accuracy;
- The data are used in accordance with the rights of the study participant;

- The data are stored securely;
- Relevant international and national guidance will be consulted.

All data held by the study team will be pseudonymised to a study number. Only the original submitting laboratory will hold the code to link back to the participant. All samples will be sent for processing under the study number only. After 6 months the original hospital will be asked to collect health data on a pseudonymised (study number only) clinical report form on all cases and a proportion of controls (CDI negative samples) identified by the central testing laboratory. Under GDPR pseudonimised data is classified as personal data. After collection of the data and verification/data querying has been completed (within one month of collection) the link will be destroyed at the local study sites, to ensure there cannot be any link to participants, rendering the data anonymous at this point. To add a further layer of protection all participating sites are also pseudonymised, to prevent link back to the site by consortium partners. The University of Leeds will hold the link back to the site code on a password protected spreadsheet on secure University of Leeds servers during the collection of the data; this will be destroyed after data collection and will not be archived.

#### Key EU legislation for human data use

Key references that govern the use of human data are listed below. This list is not intended to be all inclusive.

- Data Protection Directive 95/46/EC of the European Parliament and of the Council (1995)
- Convention for the Protection of Individuals with Regard to Automatic Processing of Personal Data (1985)
- Recommendation No. R (97) 5 on the Protection of Medical Data (1997)
- Declaration on Ethical Considerations Regarding Health Databases (2002)
- Data protection and privacy ethical guidelines of the Experts Working Group on data protection and privacy (2009)
- Article 29 Data Protection Working Party, Vademecum on Notification Requirements (2006)
- Article 29 Data Protection Working Party, Working Document on the processing of personal data relating to health in electronic health records (EHR) (2007)
- EU General Data Protection Regulation (GDPR) 2018), specifically Articles 12 (1), 13 (1) and 89 (1),

#### *Objective 1.5 Transmission model constructed from datasets collected in objectives 1.1-1.4.*

An anonymised dataset, derived from the previous objectives, will inform the transmission modelling. The dataset will be anonymous at this point, as the link-back to the participants will have been destroyed. No participant identifiable data will be included in this dataset. All data will be held against a study number based on the sample number from objective 1.1. These data may include but may not be limited to demographic information, co-morbidities, patient outcomes (mortality/morbidity), recurrence of CDI, linked clinical and laboratory tests and results. The principals of data protection discussed above in O1.3 and 1.4, are also applicable to this objective.

#### Work-package 2

# *Objectives 2.1-2.4 Collection of surveillance data from participating sites (hospital and community practices)*

Each participating centre and their associated community practices (sample source sites) will also be asked to complete a web-based questionnaire on guideline knowledge, compliance, testing policy and methodology, surveillance practices, and stratification of 'severe' patients. In addition, 10

nursing homes in each of the four regions of Europe will be asked to complete the surveillance form to address the knowledge gap with these facilities. Data will be compared to identify differences between countries and healthcare providers. Collection of surveillance data from participating sites and their associated community practices does not require approval from an ethical review board.

#### **Objectives 2.5 Evaluation of costs based on data collected from 02.1-2.4.**

The dataset used for this data analysis will be derived from objectives 2.1-2.4. This data was collected as part of surveillance and therefore does not require approval from an ethical review board.

# *Objective 2.6 Construction of cost effectiveness model based on data in 02.5 and dataset generated from work-package 1.*

An anonymous dataset, derived from the previous objectives in both work-package 1 and workpackage 2, will inform the cost-effectiveness model. No participant identifiable data will be included in this dataset. All data will be held against a study number based on the sample number from objective 1.1. These data may include but may not be limited to demographic information, comorbidities, patient outcomes (mortality/morbidity), recurrence of CDI, linked clinical and laboratory tests and results. The principals of data protection discussed above in O1.3 and 1.4, are also applicable to this objective.

# 2. COMBACTE-CDI organisational structure

#### 2.1 Funding and Sponsorship

COMBACTE-CDI receives support from the Innovative Medicines Initiative Joint Undertaking under grant agreement no 115523 115620 115737 777362 resources of which are composed of financial contribution from the European Union Seventh Framework Programme FP7/2007-2013) and EFPIA companies in kind contributions.

#### 2.2 European coordinator

The lead partner for COMBACTE-CDI is University of Utrecht; however work packages 1 and 2 are led by the University of Leeds and will be coordinated from the Healthcare Associated Infections Research Group in The University of Leeds. The European Coordinator for the main study that forms the basis for objectives 1.1-1.4 is the University of Leeds.

#### 2.2.1 European Coordinator role

- Identify National coordinators and oversee study
- Write standard operating procedures
- Write materials required for submission for ethical approval
- Design data capture sheets (manual and electronic) and databases
- Collate data from all national coordinators
- Data analysis and report writing
- Control of budget

#### 2.3 National coordinating centres

One national coordinating centre will be recruited per country. Each national coordinating centre will correspond with the European coordinator directly. Each national coordinator will receive a budget to cover participating site recruitment, obtaining in-country ethical approval and coordinating all study activities within their country including distribution of study transport

packaging to participating sites. The national coordinator will also be responsible for the payments to participating hospitals for sample collection and follow up Clinical report forms and questionnaires. A full list of national coordinators can be found at the beginning of this document.

#### 2.3.1 National Coordinator role

- Obtain ethical approval for the study in their country
- Recruit participating sites in their own country to the study
- Distribution of study transport packaging to participating sites
- Coordination of sampling from all participating sites within their country.
- Distribute CRF packs to sites
- Coordinate the distribution of surveillance forms to participating sites (and nursing homes in selected countries)
- Report to the European coordinator

#### 2.4 Participating Sites

A small fee will be paid to each participating site to cover labour costs incurred in sending the samples. An additional small fee will be payable for each CRF completed as part of the case/control study, and the completion of the surveillance form for their site and coordination of surveillance form completion (by all associated community practices) as part of work package 2.

#### 2.4.1 Participating Site recruitment

The number of participating sites to recruit for each country is shown in table 1 in the appendices. Participating sites should be selected to cover as broad a geographical area of each country as possible, with all geographical regions within a country represented (dependent upon the number of participating sites to be included). In addition, the countries selected will proportionally represent each of the four zones of Europe (North, South, East and West, as defined by the UN Geoscheme for Europe), as stark differences between hospital CDI burden in these zones was shown in the previous study. The letter to invite the site to participate should be sent to the laboratory manager/lead Clinician of the Microbiology/Pathology department of the chosen site. A copy of the template Participating Site invitation letter can be found in Appendix 2.

#### 2.4.2 Participating Site definition

A **participating site** is a hospital/laboratory facility that provides enteric testing and fulfils the criteria below.

A **sample source site** is any location that sends a sample to the participating site to be tested on the sampling day (e.g. hospital, community doctor, nursing home, mental health facility).

All participating sites must meet the following criteria:

- Sites must carry out diagnostic testing of faecal samples from both in-patients and community patients
- Sites must be able to collect residual diagnostic tissue of all faecal samples received by the laboratory on a specified date in May/June and October 2018, and export this to the UK the day after collection (transport provided)
- Sites must be able to collect prospective patient data (outcome data) linked to the faecal samples provided during the sampling period (based on a provided Case Report Form) either directly or via the **sample source site**
- Sites must be able to collect retrospective patient data (risk factor data) linked to the faecal samples providing during the sampling period (based on a provided Case Report Form) either directly or via the **sample source site**

- Sites must be able to collect data on attributable costs of CDI at their site (based on a provided Case Report Form)
- Sites must be able to provide data in regards to their CDI testing policy and methodology, CDI surveillance practices, knowledge of national CDI guidelines and their local compliance, and CDI treatment (including according to patient level risk e.g. CDI severity) (based on a provided questionnaire).

#### 2.4.3 Participating Site packs

Each participating site should be allocated a date, following the site sampling plan provided to each National Coordinator. Each participating site should be sent a pack containing; the instruction leaflet to explain how to process the samples for transport to the European Coordinator, transport materials, the sampling date and copy of the data collection sheet (sample information only) at least a week before the date of sampling. Samples should be stored at 4-8°C until transport.

#### 2.4.4 Materials required

#### 2.4.4.1 Provided by European Coordinator

- National coordinator study packs (sample collection)
  - o Site list and sampling plan
  - o Template site invitation letter
  - o National Coordinator instructions for sample collection
- Participating site study packs (sample collection)
  - Participating site cover letter following confirmation of participation
  - o Participating site sampling and shipping instructions
  - o Sample collection spreadsheet
  - CDI sample result spreadsheet
  - Template material transfer agreement
- Packaging materials for distribution to participating sites (to send samples to the European coordinator via DHL).
- National Coordinator study pack (case control study)
- Participating site study pack (case control study)
- National Coordinator study pack (surveillance study)
- Participating site study pack (surveillance study)
- Copy of UK ethical approval

Study packs will be distributed to National Coordinators prior to the relevant sub-study (sample collection/case control/surveillance).

#### 3.2.2 Provided by National Coordinator

- Completed site list and sampling plan
- Copy of in-country ethical approval

#### 3.2.3 Provided by Participating site

- Completed and signed material transfer agreement
- Faecal samples and completed CDI sample result spreadsheet
- Clinical data on case control studies (CRF completion)
- Data for surveillance questionnaire

# 3. Study methods

### 3.1 Sample collection study (objective 1.1 and 1.2)

#### 3.1.1 Study rationale

Only two studies (in the UK & the Netherlands) have determined incidence rates, clinical characteristics and outcome of community-acquired CDI (CA-CDI), both reporting CDI positivity in 1.5-2.1% of patients attending a general practitioner because of diarrhoea. Given the number of patients that may never even be tested, this may well represent an underestimate of the true incidence of CA-CDI. The burden of CDI in LTCF and its relation with that in neighbouring hospitals is largely unknown. A systematic review identified only 8 studies for critical appraisal with none containing economic evaluations of interventions. The estimated incidence of CDI in LTCF was 0.41/10,000 residents per year. ECDC initiated surveillance of HAIs and antimicrobial use in European LTCF (HALT) project, including two point prevalence surveys in >750 LTCF in ~20 European countries. This study reported HAI prevalence of 2.4-3.4%, of which 5.1% represented gastrointestinal infections; of which 18% were due to *C. difficile*. However, CDI was not surveyed systematically, and no information was collected on the diagnostic methodology. We aim to address this gap.

PCR ribotyping is the method of choice for typing *C. difficile* strains. Currently, >800 PCR ribotypes, (designated 001, 002...) are known; the reference ribotype collection is held by the co-applicant's ([name]) laboratory in Leeds, UK. Knowledge of strain distribution improves understanding of epidemiology (outbreaks), transmissions (within hospital, between reservoirs, e.g. animal to human) and potential differences in virulence. Indeed, some PCR ribotypes (e.g. ribotype 027, 078) appear more virulent, with emerging evidence that some are also more transmissible.

PCR ribotype distribution varies between European countries and over time, with some types remaining prevalent for decades (e.g. ribotypes 014, 002, 027, non-toxigenic 010) However, these studies were based on isolates from hospitalised patients collected within limited time intervals. Notably, comparable data on a European scale are lacking for CA-CDI and CDI in non-hospital settings. From studies at local or national level, it is known that different strains would be more likely associated with hospital (e.g. ribotypes 027, 176) and community (e.g. ribotypes 078, 244) infection, although there is also some overlap.

Strains collected from the main study (O1.1) will be compared, by PCR-ribotyping, along with basic clinical data. Comparisons will be made between strains identified from the community and those from hospital settings, including specific analysis of those within long-term care facilities. Comparison will be made between the strains isolated from cases and those who are colonised (no *C. difficile* toxin detected). Previous work within the consortium has shown that there is variable performance for current toxin assays for different PCR-ribotypes of *C. difficile*, but lack of a highly sensitive toxin detection method has so far hampered efforts to investigate this further. Further analyses of those strains that were isolated from patients with toxin levels that were only detectable by the innovative highly sensitive SiMoA assay will help to elucidate a correlation between certain strains and low levels of toxin produced in-vivo.

Recent data show that certain *C. difficile* strains may cause disease and yet only produce binary toxin, but not toxins A and B (A-B-CDT+ strains). These strains are likely to be missed by conventional microbiological testing which detects the main toxins A and/or B. Other binary toxin producing strains (A+B+CDT+, A-B+CDT+) are associated with increased relapse rates. More data are needed to determine the prevalence of such strains and what their true potential is to cause CDI. In addition, therefore, strains will be toxinotyped; identification of the variation in toxin genes. Comparisons will be made between those strains seen within hospital and community settings, with emphasis on

#### 3.1.2 Outcome measures

Primary outcome measure: Number of missed cases of CDI - Comparison of test result at participating site and test result at European Coordinating Laboratory (using optimised testing). Objective 1.1

Secondary outcome measures:

- Number of missed cases of CDI Comparison of test result at participating site and test result at European coordinating laboratory (using novel highly sensitive C. difficile assay for toxins A and B).
- Types of *C. difficile,* as measured by PCR-riboyping, toxinotyping and whole genome sequencing. Objective 1.2

#### 3.1.3 Sampling Criteria for sample collection study

#### 3.1.3.1 Inclusion criteria

**ALL** unformed faecal samples (takes the shape of the container and/or stick will not remain vertical when inserted into the sample) from **ALL** patients (ALL ages) sent to the microbiology department of participating sites on their allotted testing day (irrespective of test requested).

#### 3.1.3.2 Exclusion criteria

Only one sample per patient can be included

#### 3.1.4 Study methods

Two study days will be selected, and all diarrhoeal stool samples received on that day by the participating site in the study will be sent (regardless of test requested) to the European Coordinating Laboratory (Leeds), where samples will be tested for CDI using the recommended 'optimal' testing methodology (GDH/Toxin (Techlab, US) testing on the DS2, as per ESCMID guidelines), reference methods (cell-cytotoxicity neutralisation assay and cytotoxigenic culture) and a novel, Single-molecule Array (SiMoA) immunoassay platform for C. *difficile* toxins A and B. Samples will also be tested for other potential gastrointestinal pathogens (using the bioFire Film array molecular method), to investigate either co-infections or alternative cause of diarrhoea (where *C. difficile* negative). Results will be compared to those from the submitting hospital/laboratory, including if the sample was even tested. The SiMoA test will be carried out at bioMerieux (France), a COMBACTE-CDI partner, as the novel technology is currently not available elsewhere. A small portion of selected samples will be sent to BioMerieux for this purpose. They will only be labelled with the study number.

All data held by the study team will be pseudoanonymised to a study number. Only the original submitting laboratory will hold the code to link back to the patient. All samples will be sent for processing under the study number only.

All of the residual diagnostic stool samples will be processed in the laboratory facilities at the Healthcare Associated Infection Research Group (HCAI) at the University of Leeds. The HCAI laboratory is also the *Clostridium difficile* reference laboratory for the UK and has >20 years of experience in handling stool specimens and bacterial isolates derived from the samples. The laboratory follows all relevant regulatory processes for the UK, and all staff are fully trained in the relevant health and safety procedures. All work is risk-assessed for hazards (microbiological, chemical, and procedural) before commencement. Samples are handled in a class II Microbiological safety cabinet to protect the researcher.

*C. difficile* isolates collected from the study samples will be typed by various methods (PCRribotyping, toxinotyping, whole genome sequencing), to determine strain relatedness and distribution. Isolates will be processed at both the Healthcare Associated Infection Research Group (HCAI) in Leeds and the National laboratory for health, environment and food (NLZOH), in Slovenia, a COMBACTE-CDI partner. Again the NLZOH has >20 years of experience in handling the organism *C. difficile* and the laboratory follows all relevant regulatory processes, and all staff are fully trained in the relevant health and safety procedures. All work is risk-assessed for hazards (microbiological, chemical, and procedural) before commencement. All laboratory work will be performed in the facilities mentioned above, which are containment level II facilities, who comply with all local and national laboratory health and safety regulations. Both laboratories follow strict waste disposal policies to ensure the correct disposal of microbiological material, to prevent accidental environmental contamination.

In addition, NLZOH will collect contemporaneous isolates of *C. difficile* from environmental and food sources, within the same countries as the human samples. These will be typed using the methodologies described above.

#### 3.1.5 Sample size

It is impossible to accurately predict the number of samples that will be collected, as this is based on what is collected on those selected days. However, given our previous experience of collecting samples from 482 hospitals across 20 European countries during the EUCLID study, we are able to estimate that we would receive 1620 samples from the 120 hospitals included (see Table 1) on each sampling day, with an average positivity rate (for toxin positive samples) of 10%, which would give 240 toxin positive samples. The culture positive rate will likely be ~15%; 252 strains would therefore

be collected for further typing per sampling day. The number of samples and the positivity rate for CDI will be examined after the first sample day collection, to decide if the next sampling day should be carried out on one (as planned) or two days. Contingency has been added to the budget to cover the additional costs of adding a testing day to increase sample numbers.

We will aim to collect a similar number of contemporaneous isolates from the environmental and food samples.

#### 3.1.6 Data collection

In addition to the laboratory data, data will be collected on the following variables;

- Sample source sites (hospital/GP, nursing home)
- CDI test result for that sample at the submitting laboratory

#### 3.1.7 Data analysis

Results of the CDI testing at the ECL will be compared with the original result at the participating site, with 'missed' diagnoses recorded (either due to false negative result at participating site, or sample not tested at participating site). Results of 'missed' diagnoses will be compared between countries and sample source sites (hospital/GP/nursing home). In addition, the number of co-infections and alternative GI pathogens (in CDI negative samples) will be compared between countries and sample source sites, to determine difference between in-patient and community populations.

Types of *C. difficile* (by PCR-ribotyping, and toxinotyping) will be compared between countries, settings (community/hospital), cases/colonised participants and those detected by different commercial testing methodologies (optimised method vs SiMoA). Whole genome sequencing will be used to examine the true relatedness of strain types within and between settings (community/hospital). Comparison will be made between the types of *C. difficile* isolated from human, environmental and food sources. In addition, whole genome sequencing will be used to examine the true relatedness of strain types between sources.

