#### 3.5.7 Data analysis

Comparisons of knowledge and compliance with guidelines for disease detection, notification and management/control will be made between countries and healthcare settings (community/hospital). Particular attention will be focussed on the dates of policies and the length of time it takes for European/national guidance to filter down to a local level. This may highlight a possible area for improvement in guideline communications.

Comparisons between testing policies and methodologies will be made between countries and healthcare settings (community/hospital). In addition, data from 1.1 on 'missed' case rates in these settings will allow identification of 'poor practice'.

Data will be compiled on current surveillance programmes for CDI and compliance with these, in different countries and settings. This will be used to determine a 'best-practice model' for surveillance and investigate mechanisms for increasing engagement with surveillance.

Comparisons of knowledge and compliance with guidelines for treatment pathways will be made between countries and healthcare settings (community/hospital). In particular comparisons will be made of risk stratification of patients (via severity criteria) between different healthcare settings and countries. Again this will be used to determine a 'best-practice model' for risk stratification.

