#### 4.1.5 Definition of controls

Patients with CDI positive samples within the 8 weeks previous or subsequent to the Index sample date will be excluded from the control cohort, after receipt of the CRF. The target case/control ratio is 1:3, though there may be variability in this ratio due to site sample size.

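### The 'missed' label in Protocol 3.1.7 has no condition on an earlier diagnosis, so a known CDI episode that was not retested on the study day is counted as missed

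*Protocol*

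**What the plan says.** The primary outcome of the sample collection study (Protocol 3.1.2) is the number of missed cases, obtained by "Comparison of test result at participating site and test result at European Coordinating Laboratory". Every unformed stool reaching the laboratory on the study day enters, "irrespective of test requested" (3.1.3.1). The only exclusion is "Only one sample per patient can be included" (3.1.3.2). Apart from the source of the sample, the one local variable collected is "CDI test result for that sample at the submitting laboratory" (3.1.6).

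Section 3.1.7 then calls an ECL-positive stool a missed diagnosis, "either due to false negative result at participating site, or sample not tested at participating site". Missed "diagnoses will be compared between countries and sample source sites (hospital/GP/nursing home"), and under 3.5.7 the missed "case rates in these settings will allow identification of" poor practice. Section 3.2.2 also sets patients correctly diagnosed at the original hospital against missed patients when comparing mortality.

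The CRF holds relevant history. SAP Appendix 1 lists CDI tests in the six months before the index sample (item 4.1) with dates and results (4.1.1), whether the patient ever had CDI (4.6), and the local repeat-testing policy (3.2). Protocol 3.2.6 adds primary or recurrent status and treatment for the episode. Neither document uses any of these to qualify the missed label. The one look-back rule, SAP 4.1.5, concerns controls: "Patients with CDI positive samples within the 8 weeks previous or subsequent to the Index sample date will be excluded from the control cohort".

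**The concern.** Consider a patient diagnosed last week, still with diarrhoea, whose stool arrives on the study day for another test. If the laboratory does not repeat the CDI test and the ECL finds toxin, 3.1.7 records a missed diagnosis. The patient was not missed. The protocol's own account of missed diagnoses in 3.5.1, under objective 2.2, gives two causes: the clinician did not suspect CDI, or the laboratory method was inadequate. Neither applies here.

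This is a rule as written, not a detail left open, and it errs in one direction. It cannot lower the missed share and can only raise it when that share is read as patients without a diagnosis. That reading is close at hand, because 3.5.7 uses the rate to judge practice and 3.2.2 sets missed patients against correctly diagnosed ones. A laboratory that chooses not to retest known cases could look worse for that reason alone.

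**Working it through.** The plan states no figure for this quantity, so there is none to reproduce. The check is first textual, then an illustration of size.

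**Text.** Trace the known, unretested patient through the rules.

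- Inclusion (3.1.3.1): eligible, because the requested test does not matter.
- Exclusion (3.1.3.2): not removed, because only duplicate samples are.
- Data (3.1.6): the local field shows that this sample was not tested. Earlier results are not collected at this stage.
- Label (3.1.7): ECL positive and not tested locally, hence missed.

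No step intervenes.

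**Inputs for size.**

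- n = 103 CCNA-positive cases, 83 hospital and 20 community (SAP 2.1, Table 1). This is a stand-in for the ECL toxin-positive set.
- t = share of ECL positives truly missed. Not in the documents; assumed 20%, 30% and 40%.
- r = share of ECL positives with a known episode and no retest. Not in the documents; assumed 0, 2, 5 and 10%. At n = 103 the non-zero values are about 2, 5 and 10 patients.

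**Shift.** Observed share = t + r. At t = 30% the four values of r give 30, 32, 35 and 40%.

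**Sampling error of one share.** Half-width = 1.96 × √(t(1 − t)/n). At t = 30%: 1.96 × √(0.21/103) = 8.85 points. At t = 20% and 40% it is 7.7 and 9.5 points.

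**Coverage.** Exact binomial probability that a Wilson 95% interval, computed from data with expected share t + r, contains t (n = 103):

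| t | r = 0 | r = 2% | r = 5% | r = 10% |
|---|---|---|---|---|
| 20% | 95% | 91% | 74% | 31% |
| 30% | 96% | 94% | 82% | 45% |
| 40% | 94% | 92% | 79% | 42% |

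**Hospital versus community.** Half-width of a difference = 1.96 × √(t(1 − t)(1/83 + 1/20)) = 19.5, 22.4 and 23.9 points at t = 20, 30 and 40%. Even a 10-point difference in r between settings would lie inside this.

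**Denominator.** How the known patients are handled changes the corrected figure. Counted as diagnosed and kept in the denominator, they leave the share at t. Dropped altogether, they make it t/(1 − r). At t = 30% and r = 10% these are 30.0% and 0.30/0.90 = 33.3%.

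**The case against.** The best defence is that 3.1.2 defines the outcome as a comparison of two results on one sample, and 3.1.7 states what the label means. On that reading nothing is misclassified. This stands for the count as a measure of testing. It does not cover the uses in 3.5.7 and 3.2.2, where the label serves as a statement about practice or patients.

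A second defence is that r is unknown. Item 3.2 shows that a no-repeat policy was foreseen, not that it is common. This also stands: the low coverage figures depend on choosing r of 5% or 10%.

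A third is that the history is collected and 3.5.7 compares testing policies alongside the missed rates. That is true, but collecting data is not a rule for using it.

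Several stronger readings are tempting and are not supported:

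- *The burden estimate is inflated.* The number of ECL positives does not depend on the label.
- *Country rankings are distorted.* This needs repeat-testing policy to differ between countries, which the documents do not show.
- *The mortality comparison is biased.* In 3.2.2 a correct diagnosis reads naturally at patient level, and SAP 2.5 lists no missed-versus-diagnosed comparison.
- *SAP 4.1.5 contradicts 3.1.7.* The SAP rule keeps recent or later CDI out of the control group and serves another purpose. It shows only that a look-back on CRF data is workable.

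**Conclusion.** The point holds in limited form. As written, 3.1.7 counts a known, unretested episode as a missed diagnosis, contrary to the protocol's own description of what a missed diagnosis is. The missed share, when read as undiagnosed patients or used to identify poor practice, is biased upward by r and never downward.

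The size cannot be fixed from the documents, and r may be near 0. At n = 103, r = 2% would hardly matter, while 5% to 10% would mislead the overall figure. Setting comparisons at this size are descriptive whatever r is. These statements assume t between 20% and 40% and take the CCNA-positive set as a proxy for the protocol's GDH/toxin-positive set; the documents do not show that the two coincide.

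It should be fixed because the bias runs one way in a primary outcome and the data needed are already planned. Confidence is medium because r is unknown.

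**What to change.** 1. Keep the sample-level count as the primary outcome, and state in 3.1.2 and 3.1.7 that it is sample-level.
2. Add one sensitivity analysis, labelled as added after sampling. Among ECL-positive, locally untested patients, use items 4.1 and 4.1.1 to identify those with a positive CDI result within a stated window before the index sample, supported where recorded by item 4.6 and the Protocol 3.2.6 items. The 8 weeks in SAP 4.1.5 is one option; add one alternative within the six months that item 4.1 covers, since a wider window takes in more possible recurrences.
3. Count these patients as already diagnosed: out of the missed numerator, kept in the ECL-positive denominator.
4. Report the number unclassifiable. Give results overall and by hospital/community; country figures should be descriptive only, with 2 to 22 planned sites per country (Protocol Appendix 1).
5. State in 3.2.2 that a correct diagnosis is judged per episode, so these patients do not enter the missed group.
6. State which positive set is used: the protocol's GDH/toxin-positive cases or the SAP's CCNA, Simoa and culture or gene categories.

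The cost is a few sentences, one SAP paragraph and a short table, with no new samples or CRF items. The analysis must wait for the 6-month CRF and depends on its completeness; retrospective data are marked Maybe for one of 12 countries. Primary or recurrent status appears in Protocol 3.2.6 but not in the SAP Appendix 1 table, so classification will rest mainly on the 4.1.1 dates. Protocol 3.2.1 itself notes that a recurrence may be diagnosed empirically or by another laboratory. Such diagnoses may go unrecorded, so some upward bias can remain and the remaining group should not be called undiagnosed.
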